7.1.3. FACIT-Fatigue Scale

If there are missing responses to items, the following approach will be taken: If more than 50% of the items are non-missing, the score will be prorated by multiplying the sum of the subscale by the number of items in the subscale, then dividing by the number of items actually answered. This can be written as:

Prorated FACIT-Fatigue score = [Sum of item scores] x 13□□ [N of items answered]

The score is only considered valid if more than 50% of the items are answered. Therefore if 50% or more of the items have a missing response, the FACIT fatigue score will be set to missing.

7.1.4. WPAI

A domain score can only be calculated if none of the required items have missing data. If any of the required items have missing data the domain score will be set to missing. Missing data will not be imputed.

8. STATISTICAL METHODOLOGY AND STATISTICAL ANALYSES**8.1. Statistical methods****8.1.1. Logistic Regression Analysis**

The potential role of several baseline clinical and biochemical parameters as independent predictive factors of remission or LDA will be investigated using logistic regression. The potential predictive factors to be considered are described in [Section 6.4](#).

The effect of each factor will firstly be tested with a univariate logistic regression model. All potential factors with a p-value resulting from univariate analysis less than 10% will then be included in a multivariate model, along with any factors considered important from a clinical point of view. Predictive factors and their interactions will be chosen using a backward (step-down) selection. Predictive factors chosen will be those which have a p-value less than 5%. In the case of a significant interaction, all individual components of the interaction will be “forced” in the model, whether they are statistically significant or not.

The SAS procedure PROC LOGISTIC will be used to perform the logistic regression analyses.

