9.5. Study Size

The primary objective of this study is to identify factors predictive of remission or LDA at month 6 of treatment. This will be investigated using a logistic regression model. For the purposes of the sample size, we will consider the LDA response rate.

Peduzzi et al suggest that such an analysis requires at least 10 events (ie, responders) per variable proposed in the model. The minimum number of subjects to include in the study can therefore be estimated using the following formula:

$$N = 10 k/p$$

where p is the smallest of the proportions of responders or non-responders in the population and k the number of covariates.

Based on the results of previous studies, eg, A3921187 we would expect an LDA response rate of 50% at 6 months and assuming that the primary analysis will include ten covariates, it will be necessary to observe 100 events in approximately 200 patients (ie, 100 events/0.50).

It is expected that the amount of missing data and drop-outs will be minimal in this study, so no allowance has been made for this in the sample size calculation.

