9.7.3. Efficacy Analysis

9.7.3.1. Primary Analysis

The primary analysis will investigate the potential role of several baseline clinical and biochemical parameters as independent predictive factors of remission or LDA at month 6 of treatment, assessed by DAS28-4 (CRP) <2.6 and DAS28-4 (CRP) <3.2, respectively and will be calculated as follows:

$$\begin{aligned} \text{DAS28-4 (CRP)} = & 0.56 * \sqrt{(\text{TJC28})} + 0.28 * \sqrt{(\text{SJC28})} + 0.36 * \ln(\text{CRP in mg/l} + 1) \\ & + 0.014 * \text{PtGA in mm} + 0.96. \end{aligned}$$

This will be investigated using logistic regression. The potential predictive factors that may be considered include:

- Age;
- Gender;
- Weight;
- Smoking history;
- Time (years) from RA diagnosis;
- Serology: RF, ACPA;
- Previous biologic DMARD use (number);
- Current concomitant treatment;
- Glucocorticoid dose;
- csDMARDs: number and dose;
- Acute phase reactants: ESR and CRP;
- DAS28-4 (CRP) score;
- HAQ-DI score;
- CDAI;
- Lipids (LDL);
- Hb levels.

The effect of each factor will firstly be tested with a univariate logistic regression model. All potential factors with a p-value resulting from univariate analysis less than 10% will then be included in a multivariate model, along with any factors considered important from a clinical point of view. Predictive factors and their interactions will be chosen using a backward (step-down) selection. Predictive factors chosen will be those which have a p-value less than 5%. In the case of a significant interaction, all individual components of the interaction will be “forced” in the model, whether they are statistically significant or not. It is anticipated that the primary model will include approximately ten covariates.

Full details, including methods for handling missing data, will be provided in the SAP. For the primary endpoints of remission or LDA, a non-responder imputation will be used for patients who have missing data at month 6.

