6.4. Covariates

The following potential risk factors will be included as covariates in the logistic regression analyses of remission and LDA:

- Age:
Age at baseline will be included as a continuous covariate.
- Gender (male/female).
- Weight:
The weight (kg) at baseline will be included as a continuous covariate.
- Smoking history:
Smoking history will be included as a categorical covariate with five levels:
 - Never;
 - History but cessation of more than 3 years;
 - History but cessation of less than 3 years; Smoker, regular (≥ 1 cigarette/day); Smoker, low (< 1 cigarette/day).

If there are issues with the convergence of the model using the above categories, these will be collapsed into the following 3 categories:

- Never;
- Ex-Smoker; Smoker.

PFIZER CONFIDENTIAL

- Duration of Disease at Baseline:
Time (years) from RA diagnosis to inclusion in the study will be included as a continuous covariate.
- Serology at Baseline:
• Rheumatoid Factor (RF) will be included with two levels: positive and negative.
• Anti-citrullinated protein antibodies (ACPA) will be included with two levels: positive and negative.
- Previous DMARD use (number):
The number of previous biological (bDMARDs) will be included as a continuous covariate. See Appendix A1.2 for details of drugs to be considered as bDMARDs.
- Current concomitant treatment:
Two covariates will be fitted, one for the most common concomitant treatment (Yes/No) and one for the second most common concomitant treatment (Yes/No).
- Glucocorticoid dose:
The Glucocorticoid dose at baseline will be included as a continuous covariate.
- csDMARDs:
• The number of current conventional synthetic DMARDs (csDMARDs) at baseline will be included as a continuous covariate. See Appendix A1.2 for details of drugs to be considered as csDMARDs.
- The dose of csDMARDs at baseline will be included as a continuous covariate.
- Acute phase reactants:
ESR and CRP at baseline will be included as continuous covariates.
- DAS28-4 (CRP) score:
• DAS28-4 (CRP) at baseline will be included as a continuous covariate. This will be calculated as outlined in [Section 6.1.1](#).
- HAQ-DI score:
The HAQ-DI score at baseline will be included as a continuous covariate. This will be calculated as outlined in [Section 6.1.2.3](#).
- CDAI:
CDAI at baseline will be included as a continuous covariate. This will be calculated as outlined in [Section 6.1.2.4](#).
- Lipids:

PFIZER CONFIDENTIAL

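### Predictors are chosen by univariate screening and backward elimination with no internal validation, so the final model will be over-optimistic and stable factors cannot be told from chance ones

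*SAP*

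**What the plan says.** SAP 8.1.1 and Protocol 9.7.3.1 describe the same procedure.

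- Each factor is tested alone, and "All potential factors with a p-value resulting from univariate analysis less than 10% will then be included in a multivariate model".
- A second route into that model is judgement: "along with any factors considered important from a clinical point of view". These factors are not named.
- "Predictive factors and their interactions will be chosen using a backward (step-down) selection". Terms are kept at p<0.05, and the components of a significant interaction are forced in. Candidate interactions are not listed.

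The pool is in SAP 6.4, introduced by "The following potential risk factors will be included as covariates in the logistic regression analyses of remission and LDA". On smoking it says: "Smoking history will be included as a categorical covariate with five levels".

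The study size in Protocol 9.5 rests on two assumptions: "we would expect an LDA response rate of 50% at 6 months" and "assuming that the primary analysis will include ten covariates". Protocol 9.7.3.1 likewise anticipates a primary model of about ten covariates.

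The procedure is run for remission and LDA at month 6 (primary) and again at month 12 (secondary). Neither document mentions bootstrap, cross-validation, split samples, shrinkage, AUC, calibration or multiplicity adjustment. SAP section 4 states that there are no formal hypotheses or decision rules.

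**The concern.** Naming factors that predict response is the study's only primary objective, and the rationale in Protocol section 7 is personalised treatment. When the same 200 patients are used to screen, to select and to estimate, two things follow. Some retained factors may be noise. Those that are real are kept more often when chance has inflated their estimates. Both effects make the model look better than it would in new patients.

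No planned output shows how large these effects are. A reader given the final list could not tell a factor that would be chosen in nearly every resample from one chosen by luck. The limitations in Protocol 9.9 cover selection bias, the lack of a control group and missing data, but not overfitting.

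**Working it through.** **1. The plan's own figure.** Protocol 9.5 uses N = 10k/p. With k = 10 and p = 0.50, N = 10 × 10 / 0.50 = 200. This reproduces the stated size.

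**2. The pool that selection starts from.** Counting SAP 6.4: age, gender, weight, smoking, disease duration, RF, ACPA, number of bDMARDs, two concomitant treatments, glucocorticoid dose, csDMARD number, csDMARD dose, ESR, CRP, DAS28-4 (CRP), HAQ-DI, CDAI, LDL and Hb. That is 20 factors. Smoking takes 4 parameters, so there are 19 + 4 = 23.

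- Events per factor: 100/20 = 5.0. Events per parameter: 100/23 = 4.3.
- The plan's formula applied to the pool: 10 × 20 / 0.50 = 400, or 10 × 23 / 0.50 = 460.

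Ending with ten or fewer factors chosen on the same outcome data does not restore ten events per variable, so the study size gives no protection here.

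**3. Chance of a false predictor, by formula.** With m independent null candidates tested at 0.05, the chance of at least one is 1 − 0.95^m: 40% for m = 10, 51% for m = 14, 56% for m = 16 and 64% for m = 20. With 20 nulls, about 20 × 0.10 = 2 pass the screen and about 20 × 0.05 = 1 is expected to survive.

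**4. Simulation of the written procedure, main effects only.** N = 200, 50% response, 20 independent factors, assumed odds ratio 1.5 per SD for each true factor, 600 to 1,500 runs per scenario for most figures. Repeated runs differ by a few percentage points.

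| True factors among 20 | At least one false predictor, per model |
|---|---|
| 0 | about 63% |
| 4 | 51–55% |
| 7 | 42% |
| 10 | 31–36% |

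When true factors exist, the simulated values fall somewhat below the formula, because a null factor must pass both the unadjusted screen and the adjusted backward step.

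Sensitivity, also main effects: all null with correlated factors, 62%; the same at an assumed 30% response rate, 59%; three true factors, 54% if independent and 61% if correlated (the last counts proxies of a true factor as false).

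**5. Optimism.** New-patient AUC was measured in independently generated data.

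- 4 true factors: apparent AUC about 0.72 against 0.66, a gap of 0.06. Retained true odds ratios average about 1.66 against 1.5. On the log scale, ln 1.66 / ln 1.5 = 0.507/0.405 = 1.25, so the effect is overstated by about a quarter.
- 3 true factors: about 0.70 against 0.63–0.64, with a calibration slope of about 0.65.
- All null: 0.61–0.62 against 0.50 in the runs that select something. Counting empty models as 0.50 gives 0.636 × 0.616 + 0.364 × 0.50 = 0.57.

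**6. Interactions.** With 4 true factors, adding all pairwise interactions of the screened factors and forcing their components raised runs with a false term from 51% to 65%. Mean false terms, counting forced components, rose from 0.67 to 1.5. AUC was 0.73 against 0.65 in new patients.

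**The case against.** The best defence is that this is exploratory work. With no formal hypotheses, no error guarantee is broken. The aim is to identify factors, not to issue a risk score, so AUC and calibration slope are less central than selection frequency. That stands, and it limits the severity. It does not remove the need for some measure of stability, since the list of factors is itself the primary result.

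Four stronger readings are tempting, and the documents do not support them.

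- A reader might infer that a false predictor is likely whatever the truth. For one main-effects model, a chance above one half needs about 14 or more of the 20 candidates to be null. Protocol section 7 reports earlier evidence that response may vary with baseline CRP, and CRP, DAS28-4 (CRP) and CDAI are all candidates, so the all-null case is an extreme.
- A reader might multiply the risk by four models. Remission (<2.6) is nested within LDA (<3.2) in the same patients with the same candidates, so these are dependent repeats, and month 12 is secondary.
- A reader might infer that p-values and odds ratios will be presented as if the model had been fixed in advance. The SAP specifies selection, not presentation, and its table shells are in a separate document (SAP section 9).
- A reader might count 45 pairwise interactions. That needs ten factors to reach the multivariable step. If all candidates were null, about two would pass the screen, giving one pair, before any added on clinical grounds.

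**Conclusion.** The concern holds in a limited form. The plan selects factors and unlisted interactions from 20 candidates on about 200 patients and provides nothing by which to judge the result. Over-optimism appeared in every scenario examined. It is the firm part of the finding: with 4 true factors, an AUC gap of about 0.06 and odds ratios near 1.66 for a true 1.5.

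The chance of a false predictor depends on how many candidates are truly null, which is unknown. It runs from about 63% down to 31–36% across the cases tabulated, and open interactions add to it.

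The odds ratio of 1.5, the numbers of true factors, the correlation structure and the 30% response rate are assumptions. Only the 50% LDA rate, the 200 patients, the thresholds and the candidate list come from the documents. Entry by clinical judgement could not be simulated because those factors are not named. This should be changed, but it does not invalidate the study.

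**What to change.** Keep the selection procedure and add to SAP 8.1.1:

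- bootstrap internal validation that repeats the whole procedure in each resample (screen, backward step and interactions), not just a refit of the final model;
- beside the final model, each factor's selection frequency, the optimism-corrected AUC and the calibration slope.

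Preferably also limit candidate interactions to a short list fixed before outcome data are examined.

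The bootstrap and its outputs cost SAP text, computing time and less favourable reported performance. They need no new patients, visits or data. Restricting interactions alters the stated primary method. Protocol 9.7 says that major modifications of primary endpoint analyses would be reflected in a protocol amendment, so the sponsor should check whether one is needed for that part.

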9.2. Setting

The planned recruitment period is 12 months. With planned observation duration of 12 months per patient, the entire study would thus last for 24 months at maximum. The study is to start in May 2020 and will be ended in May 2022. Overall, about 200 patients in 19 centres are to be included in this non-interventional study. A patient will be followed up until the end of the planned study duration, regardless of any missing intermediate visits, as well as treatment changes during the course of follow-up.

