9.4.1. Study Procedures

Consecutive subjects attending will be included if they fulfil all selection criteria for the study and are started on treatment with tofacitinib for moderate to severely active rheumatoid arthritis.

All visits shall be scheduled according to clinical practice. Within this study 4 visits may be documented and one follow-up telephone communication at least 28 days after the last clinic visit for those patients with an ongoing treatment-related AE should be conducted. At each visit subjects will undergo procedures in compliance with the country label and as per standard of care. In order to collect comparable study data, visits occurring +/- 14 days of the scheduled visit date can be documented. If a patient misses one or more pre-planned study visits the patient can remain in the study.

After a training session the sites will get access to the eDCT where the data and findings of the patient are documented. Also a folder with questionnaires will be provided. The collection of all data is prospective. Dose and duration of treatment should be based on clinical and individual needs and are determined by the treating physician. To provide accurate information of the treatment, the initial tofacitinib dose and all changes and the reasons for changes are documented during the course of the evaluation. The concomitant medication is determined by the treating physician and is registered in the eDCT.

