9.4.24. C-reactive Protein (CRP)

The CRP shall be analysed by a local laboratory as per standard clinical practice and documented at each visit (visits 1-4). It will be used in the calculation of several efficacy parameters.

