2.2. Study Population

The study population consists of patients with RA treated with Tofacitinib in Greece. *Overall, about 200 patients in 19 centres are to be included in this non-interventional study.*

The planned recruitment period is 12 months. With a planned observation duration of 12 months per patient, the entire study would thus last for 24 months. A patient will be followed up until the end of the planned study duration, regardless of any missing intermediate visits, as well as treatment changes during the course of follow-up.

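### The remission and LDA logistic models ignore centre, so for predictors that vary between the 19 centres p-values can be too small and centre differences can be selected as patient predictors

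*SAP*

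**What the plan says.** SAP 2.2 states that "about 200 patients in 19 centres are to be included"; Protocol 9.2 gives the same numbers. For the analysis of remission and LDA, SAP 8.1.1 says "The SAS procedure PROC LOGISTIC will be used to perform the logistic regression analyses". Each factor is screened univariately at p below 10%, and backward selection then keeps those with p below 5%.

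The candidate factors are listed in SAP 6.4, and all describe the patient. Centre is not among them. The summary of analyses in SAP 8.2.5 refers all four logistic models (remission and LDA, Month 6 and Month 12) to that list and names no stratum. No random centre effect or cluster-robust variance appears elsewhere in either document, and the mixed models in SAP 8.1.2 account for repeated measures within subject only. The limitations in Protocol 9.9 do not mention centre.

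Some inputs are local. On CRP, which enters both the DAS28-4 (CRP) endpoint and the predictor list, Protocol 9.4.24 says "The CRP shall be analysed by a local laboratory as per standard clinical practice". ESR is also measured locally (Protocol 9.4.25). On treatment, Protocol 9.4.1 says "The concomitant medication is determined by the treating physician".

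**The concern.** Patients of one centre share a laboratory and, probably, prescribing habits. Two problems can follow.

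- **Correlation.** If response levels differ between centres and a predictor also differs between centres, the ordinary logistic standard error for that predictor is too small. The 10% screen and the 5% selection rule then admit null predictors more often than stated.
- **Confounding.** If centres with a higher mean of the predictor also have higher or lower response for other reasons, the pooled model attributes that centre difference to the patient's value of the predictor.

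The candidates most open to this are CRP, ESR, glucocorticoid dose, csDMARD number and dose, and concomitant treatment. The primary objective is to name independent predictors of response. A factor selected because of how a centre measures or prescribes would be reported as a property of the patient.

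**Working it through.** **The plan's own figure.** Protocol 9.5 applies a rule that "requires at least 10 events (ie, responders) per variable proposed in the model", with N = 10k/p. It says "we would expect an LDA response rate of 50% at 6 months", "assuming that the primary analysis will include ten covariates". So N = 10 × 10 / 0.50 = 200, which reproduces the stated figure. The calculation has no allowance for clustering.

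**Inputs.** Mean centre size m = 200/19 = 10.53, from the documents. The outcome ICC and the predictor's centre ICC are not in the documents, so the values below are assumptions shown as a range.

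**Approximation.** Variance inflation for an ordinary logistic coefficient is V = 1 + (m − 1) × ICC(outcome) × ICC(predictor). The true error of a nominal 5% test is 2 × [1 − Φ(1.96/√V)].

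- 0.05 and 0.3: V = 1 + 9.53 × 0.015 = 1.143, error 6.7%.
- 0.10 and 0.3: V = 1 + 9.53 × 0.030 = 1.286, error 8.4%.
- 0.20 and 0.5: V = 1 + 9.53 × 0.100 = 1.953, error 16.1%.
- Predictor ICC 0: V = 1, error 5.0% whatever the outcome ICC.
- Outcome ICC 0.01 with a predictor set wholly by the centre (predictor ICC 1): V = 1.095, error 6.1%. The problem is then negligible.

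**Simulation.** The set-up was 19 centres, about 200 patients, 50% response, a random centre intercept (ICC on the latent logistic scale), one null predictor, an ordinary Wald test and 4000 runs per setting. The Monte Carlo standard error at 5% is √(0.05 × 0.95/4000) = 0.3 points.

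| Outcome ICC | Predictor ICC | 5% test, equal centres | 5% test, unequal centres | 10% screen, equal / unequal |
|---|---|---|---|---|
| 0.05 | 0 | 4.8% | 4.3% | 9.9% / 9.1% |
| 0.05 | 0.3 | 6.1% | 7.2% | 11.5% / 12.9% |
| 0.10 | 0.3 | 8.1% | 8.5% | 14.8% / 15.8% |
| 0.20 | 0.5 | 12.8% | 15.6% | 19.7% / 23.5% |

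The formula needs an ICC on the observed scale, where a latent 0.05 is about 0.040. That is one reason why it runs slightly above the equal-centre results.

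**Confounding added.** Here the centre's predictor mean correlates 0.5 with its response level, and there is no within-centre effect (2000 runs per setting).

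- 0.05 and 0.3: declared significant in 13.3% of runs, mean spurious odds ratio 1.11 per SD.
- 0.10 and 0.3: 18.5%, odds ratio 1.16. Smaller simulations of the same setting gave 17 to 21%.
- 0.20 and 0.5: 44.1%, odds ratio 1.30. This is the extreme of the grid.

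**What repairs it.** Conditioning on centre gave 3.2 to 5.8% in 500 runs per setting and 3.9 to 5.2% in 800, with and without confounding. A plain random centre intercept (400 runs per setting) held 4.8 to 5.5% without confounding. With the 0.5 correlation it still rejected in 12 to 16% of runs, against 22 to 45% for the ordinary model (outcome ICC 0.10 to 0.20, predictor ICC 0.3 to 0.5).

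**The case against.** The strongest reply is that the size is unknown. With no ICCs in the documents, an outcome ICC of 0.05 or less moves a 5% test by at most about two points at predictor ICC 0.3. SAP 4 also declares no formal hypotheses or decision rules, so the work is exploratory. The first part stands and limits the size. The second does not remove the point, because the p-value thresholds in SAP 8.1.1 decide which factors are reported as independent predictors.

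A second reply is that PROC LOGISTIC can stratify by centre. That is correct: the gap is the missing specification, not the choice of procedure.

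A third is that stratifying gives up information when Protocol 9.5 has no reserve. That is fair, and is why the fix refits the final models and does not replace the whole selection.

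A reader might go further than the documents allow in four ways.

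- **All p-values are too small.** Age, gender, weight, RF and ACPA need not vary by centre, and then they keep their nominal error.
- **Joint assessors are known to differ by centre.** Protocol 9.4.15 mentions a joint assessor without saying who it is. Local assessors are a plausible inference, not a stated fact.
- **Drug predictors are simply centre habits.** Protocol 9.4.1 ties tofacitinib dose and duration to individual need and leaves concomitant medication to the treating physician. Prior bDMARD use may predate the centre.
- **The response rates need centre-adjusted intervals.** SAP 8.1.4 plans only counts and percentages, so there is no planned interval to correct.

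**Conclusion.** The concern holds in limited form. All four logistic models treat about 200 patients from 19 centres as independent. For predictors that vary by centre this can make p-values too small and can present centre differences as patient predictors. Both a centre effect on the outcome and centre variation in the predictor are needed; if either is absent, the nominal error is kept.

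The size rests on assumed ICCs and ranges from nothing to material. The settings above 10% should not be read as the expected result. Whether centre in fact confounds any listed predictor cannot be known from the documents. The point is worth correcting because it bears on the primary objective and the remedy is cheap, but it does not invalidate the design.

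**What to change.** In SAP 8.1.1, keep the planned screening and backward selection and add a refit of each final Month 6 and Month 12 model that separates within-centre from between-centre association. There are two acceptable forms:

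- PROC LOGISTIC with a STRATA statement for centre, with very small centres pooled by a rule set in advance; or
- a random centre intercept with predictors centred within centre.

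Show the pooled and centre-conditioned odds ratios and intervals side by side. Report as patient-level predictors only those whose association persists, and flag the rest as possibly centre-driven. State beforehand what counts as persisting, so that a similar odds ratio with a wider interval is not confused with one that shrinks towards 1.

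A plain random intercept alone is not enough, because it leaves between-centre confounding. Fixed terms for centre would add 18 parameters; under the plan's own rule that needs 10 × 28 / 0.50 = 560 patients.

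The cost is SAP wording and code, with no new data or visits. Intervals will be somewhat wider, and centres with all or no responders drop out of the conditional model. At 50% response, with patients taken as independent, the chance of this is 2 × 0.5^10 = 0.2% for a centre of 10 but 2 × 0.5^3 = 25% for a centre of 3, which is why small centres should be pooled.
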